## **5.0 STUDY DESIGN AND METHODS**

### **5.1 Design /study type**

This is a one-time, cross-sectional, patient survey study where the overarching goal is to evaluate the benefits and harms of currently accepted GCC vs. AS (including patients with DCIS undergoing AS, as well as patients with ADH or LCIS/ALH as a proxy) for DCIS.

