***Lobular neoplasia (LN) is another example of a risk marker for invasive breast cancer.***

Lobular neoplasia is characterized by the proliferation of uniform rounded cells which arise from the terminal ductal lobular units. These cells have relatively little cytoplasm, are dis-cohesive, and may spread along the ducts in a Pagetoid fashion. If the cells occupy and distend more than 50% of the acini, the condition is termed lobular carcinoma in situ (LCIS), otherwise it is termed atypical lobular hyperplasia (ALH). Although the distinction between the two conditions is one of degree, the more extensive changes seen in LCIS are associated with a higher risk of subsequent malignancy than occurs in ALH. Previous studies have suggested that LN is predominantly a condition found in pre-menopausal women. A study of women registered on the Surveillance, Epidemiology and End Results (SEER) database in the US shows a 38% increase in the incidence of what in the SEER database is termed LCIS between 2000 and 2009, from 2.0/100,000 to 2.75/100,000 in females aged 18-80. Two previous studies of the SEER database suggest that there has been a three to four-fold increase in LCIS diagnoses since 1978 (women with ALH were not included in these studies), predominantly among post-menopausal women. This increase is explained, at least in part, by the increasing use of screening mammography and the increasing proportion of women who undergo percutaneous needle biopsy in the investigation of screen-detected abnormalities, particularly microcalcifications.

A recent study of 1060 women with LCIS reported bilateral synchronous LCIS in only 2% of cases, and in the same series none of the 56 women who underwent bilateral prophylactic mastectomy were reported as having bilateral LN, although six had contralateral occult cancers (three invasive carcinomas and three DCIS). Lobular neoplasia has long been regarded as a marker for an increased risk of subsequent malignancy rather than as a precursor. The known increase in breast cancer risk in both breasts has been cited as a justification for this view. However, more recently, the hypothesis has emerged that, at least in some women, LN may be a non-obligate precursor of invasive malignancy. The risk of malignancy appears to be higher in LCIS than ALH, estimated to be 8-10 times and 4-5 times background incidence respectively.

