***Current gaps in evidence.***

In 2009, the National Cancer Institute (NCI) convened a State-of-the-Science conference that identified the most critical research questions around DCIS, including investigations on the impact of DCIS on QOL and trials evaluating the comparative effectiveness of DCIS treatment strategies. Further, the American Cancer Society and National Institutes of Health (NIH) published the summary of an NCI DCIS Workshop in 2010 that reviewed current issues in DCIS and identified risk communication as a priority area for future study. However to date, data remain lacking in all of these areas.

Current treatment options routinely offered for DCIS include surgery (lumpectomy or mastectomy),

radiation (radiation or none) and hormonal therapy (Table 1). Increasingly, some women choose to undergo bilateral mastectomy. These options constitute GCC according to National Comprehensive Cancer Network (NCCN) treatment recommendations. Between 1991 and 2010, 23.8% of women diagnosed with DCIS in the United States underwent mastectomy, 43% lumpectomy with radiation, and 26.5% lumpectomy without radiation, based on data from the Surveillance, Epidemiology, and End Points Registry. Among the 97% of women with DCIS treated with GCC, neither randomized trials or retrospective studies to date have shown a survival advantage of any treatment option over another. To date, none of the treatment options has ever been compared to AS.

**Table 1. Guideline concordant care (GCC) and Active surveillance (AS) options for DCIS.** All treatments offered as part of published guidelines mandate surgical excision to negative margins and consideration for adjuvant radiation or endocrine therapy.

	Intent	Surgery	Radiation	Endocrine Therapy
Guideline- Concordant Care (GCC)	Treatment at time of diagnosis for all patients	lumpectomy	yes	yes
			no	no
		mastectomy	no	yes
				no
Active Surveillance (AS)	Treatment only for those who progress during surveillance	none	no	no
				yes

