#### **4.0 RESEARCH SUBJECT ENTRY**

All activities will be conducted through the 6 study recruitment sites, who will handle all eligibility for their own site's patients. The DFCI main study site will screen and recruit for its own patients as well as for DFCI @ SSH patients. Patients will be recruited individually to the trial. All women with DCIS, LCIS, ADH or ALH newly diagnosed between January 1, 2012 and June 30, 2017 and treated at one of the 6 designated study sites will be identified systematically at each study site using cancer registry and clinic, radiology, and pathology record review. We will collect consecutive cases in a retrograde fashion starting from June 30, 2017 to January 1, 2012 until we have collected 900 DCIS cases and 300 LCIS, ADH, or ALH cases.

In order to assess eligibility and initiate entry into the study chart review necessary for Aim 1 of the study, we will request approval of a waiver of informed consent and a waiver of HIPPA. Once approved, a research coordinator at each site will review clinic, radiology, pathology, and tumor registry lists to screen for potential candidates, and identify potentially eligible patients. We will extract the following from the medical record for potential participants:

- Name
- Contact information (i.e. mail address, phone number and/or email address)
- Age
- Race/Ethnicity
- Date and type of last biopsy
- Date and type of last surgery
- How lesion identified and relevant mammography
- Pathologic features of the disease on core biopsy (if DCIS: grade, necrosis, ER, PR/HER2 if done, size, microinvasion)
- Type of subsequent evaluation of lesion (excision, surgery etc.) and any subsequent breast pathology or procedure
- Any adjuvant treatment
- Date and vital status at last follow-up; we will plan to complement this with a National Death Index (NDI)/Institutional database look to make sure potential participants are available before contacting them.

Sites responsible for screening patients and their affiliates will use the eligibility information above for their patients to determine eligibility. We will also use these data to describe the patient population and the disease characteristics of these non-invasive breast lesions at diagnosis.

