### **6.2 Sample size and statistical power**

Importantly, published data indicate that patients undergoing lumpectomy with radiation report comparable levels of pain and sensory disturbances as those undergoing mastectomy. Thus, these treatment groups will be grouped together in the initial analysis, then a stratified analysis will be performed. Preliminary data among 582 women undergoing either lumpectomy or mastectomy indicate that the mean persistent pain intensity after breast surgery is 2.61 (DS 4.24). Given a sample size of 900 patients in the GCC group and 300 in the AS group, we will be able to detect with 90% power at a level of 0.05 (2-sided) a difference in pain intensity score of 2 (from 2.61 to 0.61), which has been deemed to be a clinically meaningful difference.

Based upon the number of unique cases diagnosed with DCIS at each site between 2010 and 2013, we estimate that at all 6 study sites combined, approximately 1500 women will have been diagnosed with DCIS between January 1, 2012 and June 30, 2017 and will be eligible to participate. Our response rate in prior survey studies has been approximately 60% using the approach we will adapt to the current study; thus, we anticipate that about 900 women with DCIS will be accrued and will complete the survey across all study sites. These patients will be matched 3:1 to participants diagnosed with ADH or LCIS/ALH undergoing active surveillance. DCIS participants will be matched 3:1 to ADH/LCIS/ALH participants, based on matching criteria of age within 5 years, year of diagnosis, and study site. Additional matching criteria such as race, income, highest education level attained, and family history of breast cancer will be considered based upon stakeholder input during the protocol preparation process.

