6.2 Sample size and statistical power

Importantly, published data indicate that patients undergoing lumpectomy with radiation report comparable levels of pain and sensory disturbances as those undergoing mastectomy.⁵⁶ Thus, these treatment groups will be grouped together in the initial analysis, then a stratified analysis will be performed. Preliminary data among 582 women undergoing either lumpectomy or mastectomy indicate that the mean persistent pain intensity after breast surgery is 2.61 (DS 4.24).⁵⁵ Given a sample size of 900 patients in the GCC group and 300 in the AS group, we will be able to detect with 90% power at a level of 0.05 (2-sided) a difference in pain intensity score of 2 (from 2.61 to 0.61), which has been deemed to be a clinically meaningful difference.

Based upon the number of unique cases diagnosed with DCIS at each site between 2010 and 2013, we estimate that at all 6 study sites combined, approximately 1500 women will have been diagnosed with DCIS between January 1, 2012 and June 30, 2017 and will be eligible to participate. Our response rate in prior survey studies has been approximately 60% using the approach we will adapt to the current study; thus, we anticipate that about 900 women with DCIS will be accrued and will complete the survey across all study sites. These patients will be matched 3:1 to participants diagnosed with ADH or LCIS/ALH undergoing active surveillance. DCIS participants will be matched 3:1 to ADH/LCIS/ALH participants, based on matching criteria of age within 5 years, year of diagnosis, and study site. Additional matching criteria such as race, income, highest education level attained, and family history of breast cancer will be considered based upon stakeholder input during the protocol preparation process.

6.3 Analysis Plan: General Approach.

We will conduct descriptive analyses to profile the samples, including examination of proportions, means, and medians, as well as estimates of variability such as standard errors, ranges, and confidence intervals. We will identify outlying observations. Continuous data distributions will be evaluated for appropriateness of scale, and normal score transformations will be used where

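### The AS comparator has no usable rule for ADH/ALH/LCIS women who had breast surgery, which can pull the primary pain contrast toward zero

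*Protocol*

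**What the plan says.** **Definition of AS.** In Table 1 (protocol Section 1.2) the AS row has no surgery and no radiation. Its intent is "Treatment only for those who progress during surveillance".

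**Who is placed in AS.** DCIS women enter by management: Section 5.5.1 seeks out those who chose AS. Proxy women are named by diagnosis:
- Section 3.0 adds ADH, ALH and LCIS to the DCIS AS group because surveillance is what is usually recommended for them.
- Section 5.1 describes the AS side as "including patients with DCIS undergoing AS, as well as patients with ADH or LCIS/ALH as a proxy".
- Section 4.0 collects consecutive cases "until we have collected 900 DCIS cases and 300 LCIS, ADH, or ALH cases".
- Section 6.3 compares GCC with a group labelled by the three lesions plus AS.

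**The one management condition.** Section 6.2 (protocol and SAP) matches the DCIS women to "participants diagnosed with ADH or LCIS/ALH undergoing active surveillance". It gives no criterion, and the next sentence, which sets the matching variables, drops the condition.

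**Surgery in proxy women.** The eligibility and exclusion lists in Section 3.0 do not mention excision or mastectomy in a proxy woman. The information is nonetheless collected. Section 4.0 extracts "Type of subsequent evaluation of lesion (excision, surgery etc.) and any subsequent breast pathology or procedure", Section 5.4 abstracts prior breast surgery, and the survey in Section 5.2 asks for surgery type. Section 1.2 also reports, from a series of 1060 women with LCIS, that "none of the 56 women who underwent bilateral prophylactic mastectomy were reported as having bilateral LN".

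**Primary endpoint and power.** The primary endpoint is pain. Section 6.2 says that with 900 GCC and 300 AS women "we will be able to detect with 90% power at a level of 0.05 (2-sided) a difference in pain intensity score of 2", that is 2.61 against 0.61.

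**The concern.** The pain endpoint is meant to capture a consequence of breast surgery, and its planning mean of 2.61 comes from 582 operated women. The comparator is useful only in so far as it represents women who were not operated on. A proxy woman who had a mastectomy, or a surgical excision of her lesion, does not fit Table 1's AS row. Nothing in the plan removes her from the AS group or separates her within it.

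The other safeguards do not reach her. The stratified analysis in Section 6.2 concerns the lumpectomy and mastectomy treatment groups. The confounders given as examples in Section 6.3 are endocrine treatment, radiation and comorbidity. Matching on age, year of diagnosis and site does not touch it. Adjusting for surgery would not help either, because surgery is what distinguishes GCC from AS.

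At stake is the size of the main result. Pain from surgery on the AS side raises the AS mean and understates the pain attributable to GCC, and a larger sample does not remove that. Two analysts could also build different AS groups from the same text.

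**Working it through.** **Inputs.** From Section 6.2: mean 2.61 and SD 4.24 after surgery, AS mean 0.61, 900 GCC and 300 AS, two-sided 0.05. From Section 1.2: 56 prophylactic bilateral mastectomies among 1060 women with LCIS. The share p of AS women who had breast surgery is not in the documents, apart from that LCIS figure.

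**1. The plan's own power.** SE = 4.24 × √(1/900 + 1/300) = 0.283. Then 2/0.283 − 1.96 = 5.12, which is power above 99.99%. The stated 90% is true only as a lower bound. The difference detectable with 90% power is (1.960 + 1.282) × 0.283 = 0.92 points.

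**2. Effect of operated proxies.** Suppose operated AS women have the plan's surgical mean and the others 0.61.
- AS mean = 2.61p + 0.61(1 − p) = 0.61 + 2p.
- Contrast = 2.61 − (0.61 + 2p) = 2(1 − p).
- If operated proxies carry only half the excess (mean 1.61), contrast = 2 − p.

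From the documents, p = 56/1060 = 5.3%, or about 16 of 300 if every AS woman had LCIS. The other rows are assumptions.

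| p | Source | Contrast, full excess | Contrast, half excess | Power, full excess |
|---|---|---|---|---|
| 5.3% | cited LCIS series | 1.89 | 1.95 | >99.9% |
| 20% | assumption | 1.60 | 1.80 | >99.9% |
| 50% | assumption | 1.00 | 1.50 | 94% |

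Allowing for the extra spread from mixing two subgroups changes the 94% only to 93%.

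**3. When power becomes an issue.** Setting 2(1 − p) = 0.916 gives p = 0.54. Below that share the study would still have at least 90% power to find a difference, but the difference found would be too small.

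**4. Price of separating operated women.** If half of the 300 were operated, 150 remain. SE = 4.24 × √(1/900 + 1/150) = 0.374. The 95% half-width goes from 1.96 × 0.283 = 0.55 to 1.96 × 0.374 = 0.73. Power for 2 points is still above 99.9% (2/0.374 − 1.96 = 3.39).

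**The case against.** **Management is not ignored.** Section 6.2 does require surveillance, and Section 3.0 describes the proxies as women managed by follow-up. Section 4.0 says sites will use the extracted information to determine eligibility, and an eligibility checklist exists that we cannot see. A reader might infer that proxies are classed by diagnosis and nothing else; that goes too far. What remains is that no printed criterion says what counts as surveillance for a proxy, and the accrual count and the matching sentence omit the condition.

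**Excision is not shown to occur in proxies.** The field in Section 4.0 covers every candidate, including DCIS women, nearly all of whom have surgery. Section 1.2 says surgery is not the recommended treatment for ADH. A reader might take the field as proof that ADH lesions are excised; it is not. The documents establish surgery only for LCIS.

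**The documented effect is small.** A move from 2.00 to 1.89 is under half a standard error, and it assumes that all AS women had LCIS. The larger shifts rest on assumed shares and on giving operated proxies the pain of a lumpectomy and mastectomy series. The 0.61 is simply 2.61 minus 2 and may already describe a mixed group. All of this stands, and it is why the size is given as a range.

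**The comparison could be of strategies.** Table 1 is captioned for DCIS, and Section 1.2 takes the recommended management of ADH and lobular lesions as the model. On that reading an excision within the usual pathway might belong to AS. This is arguable, but the plan does not say so, and Table 1 says otherwise. It supports showing both contrasts rather than only one.

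**Conclusion.** The point holds as a gap in the definition of the comparator. Table 1 excludes surgery from AS, proxies enter AS essentially by diagnosis, the single management condition is undefined, and recorded surgery is not used to form or separate the groups.

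The likely consequence is bias toward no difference in the primary pain contrast. The planned 2 points become 1.89 at the only documented share. As assumptions, they become 1.60 at 20% operated and 1.00 at 50%, or 1.80 and 1.50 with half the excess pain. These figures rest on 2.61 and 0.61 being the means with and without surgery. Since the plan treats 2 points as clinically meaningful, a moderate operated share could move the estimate below its own benchmark.

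Two stronger conclusions are not supported. A reader might infer that the study would lose its power; that needs more than about 54% of AS women operated with full surgical pain, and no document suggests such a share. A reader might also infer that anxiety, body image and symptom contrasts shift in the same way; the documents give no figures or direction for operated proxies on those outcomes.

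This should be corrected before analysis. It does not invalidate the design.

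**What to change.** In Sections 6.2 and 6.3 of the protocol and SAP:

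1. Define the AS analysis group for proxies by management received, as for DCIS, using the surgery fields in Sections 4.0, 5.2 and 5.4. State which operations count (surgery on the index lesion or for risk reduction) and how surgery after progression is classed, since Table 1 allows treatment at that point.
2. Report how many proxy women had excision and how many had mastectomy, by diagnosis.
3. Show the primary pain contrast for GCC v unoperated (biopsy-only) AS beside GCC v all AS, and report the mastectomy proxies as a separate row.
4. Reconcile Table 1, the accrual count in 4.0, the group description in 5.1 and the two matching sentences in 6.2.

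The cost is a wording change and one extra contrast. No new data are needed and no woman is dropped from reporting. The downside is a smaller AS group and a wider interval for the unoperated contrast: SE 0.374 against 0.283 if half were operated. Both analyses should be fixed in the SAP before the pain data are examined, so that the choice between them cannot depend on the result.

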### **5.2 Selection of Instruments**

***Rationale for participant selection and survey methodology.*** Although we recognize that issues of decision-making and treatment selection are more salient closer to the date of diagnosis when these decisions take place, the short timeframe of the project period limits the number of cases that could be identified and surveyed within the timeframe of the study. Therefore, we are reviewing contemporary cases diagnosed from 2012 to 2016 for eligibility. The advantage of this design is that it allows us to assess QOL after diagnosis and treatment in a large group of patients, and provides a more cost-effective approach compared to rapid case ascertainment. Moreover, this design will allow collection of our primary endpoint of persistent, rather than postoperative, pain among the participants, as well as several secondary endpoints, including health-related and psychosocial QOL, anxiety, depression, and intolerance of uncertainty among patients at a range of time in follow-up.

#### ***Survey instrument/predictors:***

**Screening questions:** We will ask participants for their first date of DCIS/ADH/LCIS/ALH diagnosis; if they have had additional breast lesions since that initial breast lesion diagnosis; and if she has had any malignancy, other than non-melanoma skin cancer. Please see Appendix E (Screening questions) for reference.

**Socio-demographics:** Women will be asked about their race, education, employment and financial status using items selected from the **Alliance Patient Questionnaire** that is currently being piloted (Alliance A191401), adapted to include an item on employment status that has been tested previously in a breast cancer population and is going to be added to the next version of the Alliance Patient Questionnaire.

**Financial burden:** We will adapt items from the National Health Interview Survey and the Cancer Care Outcomes Research and Surveillance (CanCORS) Study to assess financial burden and impact on

employment-related metrics (e.g., sick leave, unpaid time off work).

**Medical, treatment, and family history:** We will survey women regarding their treatment history, including surgery type, radiation, and hormonal therapy use and adherence, as well as family history of breast/ovarian history. Specifically, we will adapt Part 1 of the Voils two-part measure of medication adherence, which includes 3 items that evaluates the extent of non-adherence over the past week.

We will assess co-morbidities using the Self-Administered Co-morbidity Questionnaire (based on Charlson Co-morbidity Index and other comorbidity indices).

**Pain:** the presence, severity, and functional impact of pain will be recorded as the primary QOL endpoint. The primary endpoint will be highest pain severity measured on a 10-point Likert scale and Pain Burden Index as measured by the Breast Cancer Pain Questionnaire (BCPQ). The BCPQ includes assessment of pain severity, pain frequency (how many days/week), and pain location (breast, arm, side, axilla), from which a Pain Burden Index (PBI) can be calculated. The BCPQ also includes questions about other body pain, seeking medical help for pain, and painkiller use. We will also use the Brief Pain Inventory, a well-validated general measure of pain and disability, worst pain, least pain, and interference with activities.

**Knowledge:** Among patients with DCIS only, DCIS and breast cancer knowledge will be measured with items adapted from the Breast Cancer Surgery Decision Quality Instrument (BCS-DQI), an instrument designed to evaluate the quality of breast cancer treatment decisions. A series of true/false questions used in a prior survey of women with DCIS will also be used to assess knowledge of facts specific to a DCIS diagnosis and treatment; items will be adapted for patients with an ADH/LCIS/ALH diagnosis.

**Decision-making:** Treatment goals and preferences will be assessed with the BCS-DQI which includes items designed to measure individual patient goals and concerns. Four items (The SURE scale) adapted from the Decisional Conflict Scale will be used to measure patients' uncertainty about which treatment and factors contributing to uncertainty. The 5 item Decision Regret Scale will be used to measure decisional regret. Patient perception of the decision process will be assessed using an adapted version of the Control Preferences Scale. Communication with physicians and sources of information about DCIS/ADH/LCIS/ALH management options will be assessed using items from a prior study of surgical decision-making.

**Risk perceptions:** We will assess risk perceptions in women with DCIS, LCIS/ALH or ADH using questions developed by Lerman and Croyle that have previously been used to measure risk perceptions in women with DCIS. This will ultimately be compared to actual risk of their condition based on published data.

**Quality of Life (QOL):** We will use the SF-12 to measure health-related QOL. A modified 19-item version of the Breast Cancer Prevention Trial (BCPT) Symptom Checklist will be used to evaluate commonly reported menopausal symptoms. The Breast-Q, a validated instrument to evaluate outcomes following surgery, will be used to evaluate satisfaction with appearance, self-image, and sexuality. Four items from the Quality of Life in Adult Cancer Survivors (QLACS) will be adapted to evaluate frequency (1=never; 7=always) of worries about DCIS, including concerns about future breast events and death from DCIS.

**Emotional/Psychological:** To assess generalized anxiety, we will use the short-form version of the State Trait Anxiety Inventory (STAI) scale. We will use the Center for Epidemiologic Studies Depression (CES-D) Scale to evaluate depressive symptoms. Additionally, we will assess feelings of uncertainty using the Intolerance of Uncertainty Scale (Short-form), which has been used in studies of active surveillance in the prostate cancer setting.

**Time-trade-off (TTO):** We will use the QALY metric to compare tradeoffs of GCC versus AS for DCIS as determined by preference-based, as opposed to cost-based, utilities in this patient population. QALYs are derived by multiplying the length of time in a given health state with the health utility (utility weighting) of the given disease/health state. Thus, there are two primary inputs to a QALY calculation: the years of extended life with a given treatment and the health-related quality of life associated with both a pre- and post-treatment state. The general approach to determining QALYs for a given intervention uses the valuation of unaffected individuals to derive societal values for certain disease states. The time trade-off (TTO) model is a method developed specifically for use in health care evaluations and has been validated against the SG method. Respondents choose between perfect health with shorter life expectancy or poorer health but with longer life expectancy. The TTO tool will include an 8-item questionnaire.

**Treatment risk trade off:**

6 additional items adapted from a prior study of treatment preferences, that will ask women to assume a hypothetical risk of developing breast cancer and ask them to quantify the amount of risk reduction it would take for them to choose a particular surgical option (e.g., lumpectomy + radiation, mastectomy).

We anticipate that the entire one-time survey will take participants approximately 30-40 minutes to complete. The survey has been pilot tested with patient advocates to ensure that the survey content is presented in a clear and understandable format and that it is not overly burdensome to respondents. A participant's active duration on study is the length of time to complete this single survey.

